**Table 7. Interpretation of Kappa Values**

kappa	Level of Agreement
0	Equal to chance
$0 < k \leq 0.20$	Poor
$0.21 < k \leq 0.40$	Fair
$0.41 < k \leq 0.60$	Moderate
$0.61 < k \leq 0.80$	Good
$0.81 < k \leq 0.99$	Excellent
1	Perfect

### Secondary Endpoints

Device specificity and sensitivity will be defined as follows:

Sensitivity will be assessed as:

$$\text{Sensitivity} = \frac{\text{Number of subjects with Confirmed Bleeds}}{\text{Number of subjects with Confirmed Bleeds} + \text{number of False Negatives}}$$

A *Confirmed Bleed* is a bleed detected by the Saranas EBBMS that is also confirmed by CT scan and/or clinical assessment.

A *False Negative* is a bleed that is not detected by the Saranas EBBMS that *is* detected by CT scan and/or clinical assessment.

Device specificity, assessed as:

$$\text{Specificity} = \frac{\text{Number of subjects Confirmed with No Bleeds}}{\text{Number of subjects Confirmed with No Bleeds} + \text{number of False Positives}}$$

*Confirmed with no bleeds* is no bleed detected by the Saranas EBBMS that is confirmed by CT scan and/or clinical assessment.

A *False Positive* is a bleed detected by the Saranas EBBMS that is *not* confirmed by CT scan and/or clinical assessment.

The following secondary endpoints will be investigated:

- Level of agreement in bleeding detection between the Saranas EBBMS and clinical assessment or post-procedural computerized tomography will be calculated in a manner similar to specified for the primary endpoint. This analysis will be conducted in both the PP and ITT population with the clinical determination of a bleed overruling any computerized tomography or missing assessment.
- Device sensitivity in bleeding detection of the Saranas EBBMS as compared to post-procedural computerized tomography will be calculated in the PP population.
- Device specificity in bleeding detection of the Saranas EBBMS as compared to post-procedural computerized tomography will be calculated in the PP population.
- Device sensitivity in bleeding detection between Saranas EBBMS and clinical assessment or post-procedural computerized tomography will be calculated. This analysis will be conducted in both the PP and ITT population with the clinical determination of bleed overruling any computerized tomography or missing assessment.
- Device specificity in bleeding detection between Saranas EBBMS and clinical assessment or post-procedural computerized tomography will be calculated. This analysis will be conducted in both the PP and ITT population with the clinical determination of bleed overruling any computerized tomography or missing assessment.
- Relationship between level (severity) of bleed detected by the Saranas EBBMS and the severity of bleeding as assessed by computerized tomography will be investigated. Summary statistics and interclass correlations will be calculated to assess the relationship between the two variables.
- Relationship between level (severity) of bleed detected by the Saranas EBBMS and the severity of bleeding as assessed by the absolute drop in hemoglobin from baseline will be investigated. Summary statistics and interclass correlations will be calculated to assess the relationship between the two variables.
- Relationship between level (severity) of bleed detected by the Saranas EBBMS and the number of transfusions will be investigated. Tabulations, summary statistics and interclass correlations will be used to describe the relationship between these two variables.
- Relationship between level (severity) of bleed detected by the Saranas EBBMS and the severity of bleeding as assessed by VARC-2 criteria will be investigated. Tabulations, summary statistics and interclass correlations will be used to describe the relationship between these two variables.
- Relationship between level (severity) of bleed detected by the Saranas EBBMS and the occurrence of post-procedural acute kidney injury will be investigated. Summary statistics and interclass correlations will be calculated to assess the relationship between the two variables.

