Inclusion Criteria	
 
• <math>\geq 18</math> years of age
 
• Willing and capable to sign an Informed Consent form
 
• Planned large-bore endovascular procedure via the common femoral artery using a large bore catheter (<math>\geq 10</math> Fr) such as trans-femoral transcatheter aortic valve replacement (TAVR), balloon aortic valvuloplasty, complex or high-risk percutaneous coronary intervention requiring hemodynamic support device (Impella 2.5, Impella CP, and ECMO), or endovascular aortic repair (EVAR).
 

Exclusion Criteria	
 
• Subject is participating, or planning to participate in a clinical trial or study of an investigational product that may influence the data collected for this investigation
 
• Inability to access common femoral artery or vein with large bore catheters
 
• Unstable conditions such as cardiogenic shock, or ST-elevated MI
 
• Current active bleeding
 
• Pre-procedural conditions precluding the realization of a post-procedural CT scan
 
• Pregnancy
 
• Mental disability or any other lack of fitness, in the Investigator's opinion, to preclude subject's participation in or ability to complete the study as planned.
 

Statistical Methods	Descriptive statistics to be reported for each analyzed variable will include the number of observations, mean, median, standard deviation and range for quantitative variables, frequency and relative percent for ordinal and categorical variables. Level of agreement will be assessed using Cohen Kappa statistic for categorical variable, intraclass correlation for multiples categories, and Pearson correlation for continuous variables. Summary statistics will be displayed in tabular and/or graphical format. Missing data will not be interpolated for any analyses. Any hypothesis tests will be performed using a two-sided significance level of 0.05.

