[figure not shown]
Many IBC's are noted only after sheath removal. However, their trigger is thought to occur at the time of needle puncture, and small leaks are believed to occur before and during sheath placement. Early awareness of internal bleeding will allow physicians to directly and immediately address this complication and increase post-procedural vigilance in these vascular interventions.

In most cases, extensive bleeding has invariably occurred when signs or symptoms become evident. This often necessitates surgical intervention and/or blood transfusions to manage these complications. Bleeding at the vascular access site is associated with increased mortality, length of hospitalization and cost.

Presently, no marketed technology exists that can alert clinicians to an ongoing IBC immediately at its onset during a vascular access procedure. Although existing imaging

modalities such as ultrasound and computed tomography (CT) scans can identify these bleeding complications, it would be impractical and expensive to prophylactically incorporate their use as part of the clinical workflow for every procedure involving vascular access. To address this unmet need, Saranas has developed the Early Bird Bleed Monitoring System, hereinafter referred to as Saranas EBBMS (**Figure 1**), to detect an IBC in real-time without interrupting normal procedures. This technology may enable physicians to mitigate downstream consequences by addressing these complications immediately, thereby lowering long-term risks to the patient and the associated healthcare expenditures.

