## 3.5 Study Design

This is a multi-center, open-label study to evaluate use of the Saranas EBBMS for detection of access site-related internal bleeding events during large-bore endovascular procedures.

After signing consent subjects will undergo screening procedures and be scheduled for their endovascular procedure. The endovascular procedure will be performed per the institution's standard practices, with inclusion of monitoring using the Saranas EBBMS. Following completion of the procedure subjects will continue to be monitored using the Saranas EBBMS for internal bleeds for up to 8 hours. The EBBMS will then be removed. A flowchart is provided in **Figure 6**. Adverse events and device effects will be recorded from enrollment of subjects and throughout the procedure, until discharge of subjects.

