#### 4.3.3 Post-Endovascular Procedure

After completion of the endovascular procedure the following assessments and procedures will be performed:

- Saranas EBBMS monitoring for up to 8 hours post-procedure
- A non-contrast CT scan (or contrast CT if clinically indicated or preferred) to identify or confirm any bleeds
- CBC, PT, PTT, INR, creatinine and activated clotting time should be collected immediately before removal of the Saranas EBBMS
- Removal of Saranas EBBMS
- Recording of adverse events and/or device complications
- Recording of the number of units of blood transfused
- Prior to discharge, serum CBC, PT, PTT, INR and creatinine
- Subject will be discharged
- Return of device to sponsor for assessment of impedance response.

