#### **5.1.1 Recording Adverse Events**

Adverse events with an onset date following enrollment of the subject until the subject completes the study (is discharged) will be collected. Each adverse event will be followed until the adverse event has resolved or stabilized. Subjects should be encouraged to report adverse events spontaneously or in response to general, non-directed questioning. For each AE volunteered by the subject, the Investigator should obtain all the information required to complete the Adverse Event page of the CRF:

- Standard medical terminology for the AE
- Date and time of onset
- Severity of the event
- Relationship between the adverse event and the investigational product or related procedure
- Description of any subject therapy administered and actions required
- Outcome of the AE
- Whether or not the effect was serious and/or unanticipated

All AEs, regardless of seriousness, severity, or presumed relationship to study intervention must be recorded using medical terminology in the source document and on the adverse experience case report form.

Whenever possible, a diagnosis should be given when signs and symptoms are due to common etiology (e.g., cough, runny nose, sneezing, sore throat, and head congestion should be reported as "upper respiratory infection").

Each adverse event should be reported separately. For example, “nausea and vomiting” should be split into two separate events.

All AEs must be followed until resolution or until a stable clinical endpoint is reached. All measures required for AE management and the ultimate outcome of the AE must be recorded in the source document and reported to the Sponsor.

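### Reference bleeds are not tied to the time the EBBMS is active, so a bleed that starts after device removal can be scored as a False Negative

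*Combined protocol and SAP*

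**What the plan says.** **Monitoring.** Section 4.3.3 lists "Saranas EBBMS monitoring for up to 8 hours post-procedure". Section 3.5 says that after the procedure "subjects will continue to be monitored using the Saranas EBBMS for internal bleeds for up to 8 hours", and that the device then comes out. Neither sets a minimum, so the end of monitoring can differ between subjects.

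**Scoring.** Under Secondary Endpoints in Section 6.6.2, a False Negative "is a bleed that is not detected by the Saranas EBBMS that" CT and/or clinical assessment does detect. The definition does not mention onset time or whether the device was in place. Composite sensitivity and specificity are analysed in the per-protocol and ITT populations, "with the clinical determination of bleed overruling any computerized tomography or missing assessment"; the composite agreement endpoint has the same rule. Clinical assessment has no stated time window.

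**Data after removal.** Section 4.3.3 repeats the blood tests before discharge and records units transfused, with no stated cut-off. For adverse events, Section 5.1.1 says "Adverse events with an onset date following enrollment of the subject until the subject completes the study (is discharged) will be collected", with date and time of onset.

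**CT.** There is one post-procedure scan. Section 4.3.3 lists it above device removal but does not call the list a sequence. Section 5.5.2 requires only that it precede the patient's release.

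**Aim.** Section 3.5 describes evaluating the device "for detection of access site-related internal bleeding events during large-bore endovascular procedures". The definitions in Section 6.6.2 do not carry that limit.

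**The concern.** A monitor can be credited or faulted only for bleeding that begins while it is measuring. If the reference is not limited to that period, composite sensitivity partly reflects how soon a site removes the device and how long the subject is then observed. Differences between sites in removal time would look like differences in device accuracy.

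Bleeding that starts after removal is plausible on the documents' own terms. The EBBMS has its own femoral vein puncture (Section 4.3.2). The Instructions for Use (Appendix B, Section 12.3) warn of blood loss as the sheath is withdrawn and have the site closed only afterwards. VARC-2 minor bleeding in Table 4 includes an access site hematoma, so a small late event can qualify.

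Section 6.1 plans on about five bleeds, so one or two misattributed events would be visible in the results. The relationships of EBBMS level with VARC-2 class and transfusions are exposed too: subjects with no alarm but a real late bleed would weaken any association.

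**Working it through.** **Inputs.** From Section 6.1: about 100 subjects, 5 with a bleed by either method, and kappa 0.74 (95% CI 0.39 to 1.0) with two discordant pairs. From Section 6.6.2: the sensitivity formula. The number of bleeds starting after removal, *m*, is not in the documents; 0 to 3 is assumed for illustration.

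**Formulas.** Cells: *a* both positive, *b* EBBMS only, *c* reference only, *d* neither; *n* = *a* + *b* + *c* + *d*.

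- Sensitivity = *a* / (*a* + *c*)
- p_o = (*a* + *d*) / *n*
- p_e = [(*a* + *b*)(*a* + *c*) + (*c* + *d*)(*b* + *d*)] / *n*²
- kappa = (p_o − p_e) / (1 − p_e)

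**Step 1: the plan's figure.** With cells 3/1/1/95, p_o = 0.98 and p_e = (4×4 + 96×96)/10,000 = 0.9232, so kappa = 0.0568/0.0768 = 0.740. The large-sample 95% CI is 0.393 to 1.086, capped at 1.0. This matches Section 6.1. That figure compares the EBBMS with CT and contains no timing input, so this point does not change it.

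**Step 2: applying the rule.** Take a subject with no alarm, a negative CT during monitoring, device removal, and then a new hematoma noted clinically. The clinical finding overrules the CT, so the subject is a False Negative in both composite populations. A late bleed in a subject who did alarm would instead count as a Confirmed Bleed. The downward bias therefore comes from subjects without an alarm.

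**Step 3: illustration for the composite endpoints.** Five bleeds begin under monitoring and all are detected; *m* further subjects without an alarm bleed after removal. Sensitivity is shown with its exact 95% CI.

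| *m* | Cells | Sensitivity (95% CI) | p_o | p_e | kappa |
|---|---|---|---|---|---|
| 0 | 5/0/0/95 | 5/5 = 100% (47.8 to 100) | 1.00 | 0.905 | 1.00 |
| 1 | 5/0/1/94 | 5/6 = 83% (35.9 to 99.6) | 0.99 | 0.896 | 0.90 |
| 2 | 5/0/2/93 | 5/7 = 71% (29.0 to 96.3) | 0.98 | 0.887 | 0.82 |
| 3 | 5/0/3/92 | 5/8 = 63% (24.5 to 91.5) | 0.97 | 0.878 | 0.75 |

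With the reference limited to device-active time, every row returns to 5/0/0/95. The device performs identically in all four rows.

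**Step 4: which endpoints.** A bleed that starts after the scan cannot enter the CT reference. The CT-only endpoints are therefore exposed only when the scan follows removal. The composite endpoints are exposed wherever CT falls.

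**The case against.** The strongest reply is that the reference window is undefined, and a sensible analyst would read it in line with the aim, which concerns bleeding during procedures. The window is indeed undefined. But Section 6.6.2 states a complete scoring rule without that limit, and monitoring extends past the procedure, so the aim does not settle which later bleeds count.

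Four stronger readings are tempting and should not be drawn:

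- A reader might infer that reference bleeds count until discharge. Discharge is the end of adverse event collection and the occasion of the last blood tests; no section makes it the reference window.
- A reader might take "Many IBC's are noted only after sheath removal" in Section 1.1 as evidence of frequent late onset. The text goes on to place the likely trigger at needle puncture, so it describes late recognition. A bleed that began under monitoring and was noticed later is a genuine miss.
- The inclusion criteria admit "complex or high-risk percutaneous coronary intervention requiring hemodynamic support device (Impella 2.5, Impella CP, and ECMO"), and a reader might infer that support outlasts monitoring. No section says so, nor whether completion of the procedure includes removal of the support.
- Adding two late bleeds to a 3/0/2/95 version of the Section 6.1 case takes kappa from 0.74 to 0.58, below the plan's 0.6 mark. A reader might infer that the primary endpoint is at that risk. Section 6.1 concerns CT alone, so this needs CT after removal.

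Two further objections have weight. The illustrated sensitivities all lie within the exact interval for 5/5, so imprecision dominates any single result; the bias nevertheless has a predictable direction and can be avoided. And onset is often unobserved and would be judged by investigators who see the alarms, so a loose exclusion rule could flatter the device. The fix must guard against that.

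**Conclusion.** The point holds for the composite endpoints. As the definitions stand, a bleed that starts after removal in a subject with no alarm is scored as a device miss once clinical assessment finds it. This lowers composite sensitivity and agreement and can weaken the EBBMS-level relationships with VARC-2 class and transfusions. For the CT-only endpoints, including the primary kappa, the effect is conditional on the timing of the scan.

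The size cannot be fixed from the documents. Each figure in the illustration rests on an assumed number of late bleeds, five monitored bleeds and perfect detection under monitoring; one to three late bleeds would be 1/6 to 3/8 (17% to 38%) of all reference bleeds. Participation of about one day (Synopsis) limits the gap but does not close it. The conclusion that the scoring rule needs a window does not depend on the assumed rate.

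**What to change.** In Section 6.6.2, before data are seen:

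1. Define reference bleeds for the composite accuracy, agreement and severity analyses as those with onset between EBBMS activation and removal, and word False Negative to match.
2. Presume a bleed to be in-window unless prespecified, documented evidence shows that it began after removal. Examples are a negative CT or a stable CBC from the sample taken just before removal, both already collected. A negative CT clears only the time up to the scan, so the rule should say how scan time is used. A bleed that began earlier and was noticed later remains a miss.
3. Tabulate post-removal bleeds separately, and report the all-bleeds version as a sensitivity analysis.
4. Record the times of EBBMS activation, EBBMS removal and CT, which are not among the data items listed in Sections 4.3.2 and 4.3.3. Use the adverse event onset time already collected under Section 5.1.1.

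The cost is analysis wording, three time fields and one table. The downside is that onset is sometimes uncertain and is judged unblinded. The in-window presumption means that doubt counts against the device, and the all-bleeds analysis shows how much the exclusions matter. If few onsets can be placed after removal, the main result may change little. No change to clinical monitoring or device removal is proposed.

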## 1.0 INTRODUCTION

### 1.1 Background

Vascular access is necessary for any medical procedure that requires stable communication with a blood vessel. In 2010, more than 17 million procedures requiring vascular access were performed in the United States. One percent of these procedures were associated with a bleeding complication at the access site severe enough to warrant blood transfusion. These complications are difficult to detect; in most cases, extensive bleeding has occurred by the time signs or symptoms become evident.

Vascular access is most commonly achieved by using a hollow-bore needle to puncture the vessel, then introducing a hollow sheath into the vessel via the Seldinger technique. The sheath provides the operator with a stable means of introducing and removing devices such as balloons and stents (in cardiac, vascular, or interventional radiology procedures), infusing medications (in chronic chemotherapy or antibiotic therapy), filtering blood (in hemodialysis), or removing blood for analysis (in the assessment of hospitalized patients, especially those who are critically ill).

The single most frequent complication associated with any procedure involving vascular access is an internal bleeding complication (IBC) at the site where the needle initially enters the blood vessel. Often, during initial vessel puncture, the physician may accidentally penetrate the wall of the vessel, initiating an IBC. Bleeding is further aggravated by the fact that patients undergoing these procedures are often receiving high-dose of anticoagulant therapy.

In a recent review, Vavalle and Rao summarized key studies and registry data involving IBC's in patients undergoing percutaneous coronary interventions and showed that any degree of procedural bleeding is associated with significantly increased risk of ischemic injury and mortality. In a three-hospital registry (n=10,974) described by Kinnaird et al, 5.4% of the patients had major bleeding (Thrombolysis in Myocardial Infarction [TIMI] classification) and received transfusions. In the National Heart Lung and Blood Association (NHLBI) registry (n=6,656), 1.8% of the patients had access site hematomas that necessitated transfusion. In the Global Registry of Acute Coronary Events (GRACE) (n=24,045), there was a 3.9% incidence of major bleeding; almost a fourth of these hemorrhages (23.8%) occurred at the vascular access site.

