**Minor bleeding**

- Any bleeding worthy of clinical mention (e.g. access site hematoma) that does not qualify as life-threatening, disabling, or major

---

*\*Given that one unit of packed RBC typically will raise the hemoglobin concentration by 1 g/dL, an estimated decrease in hemoglobin will be calculated.*

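### The hemoglobin-drop secondary endpoint has no transfusion term, so it understates loss in any subject given red cells between the two samples, although Table 4 already holds a conversion

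*Combined protocol and SAP*

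**What the plan says.** The synopsis and sections 3.2.2 and 6.3 list, as a secondary endpoint, the relationship between device level and bleeding severity measured by the absolute hemoglobin drop. Section 6.6.2 adds only that the drop is taken from baseline ("the severity of bleeding as assessed by the absolute drop in hemoglobin from baseline will be investigated") and that summary statistics and correlations will be calculated. It gives no transfusion term, no rule for subjects transfused before the follow-up sample, and no statement of which samples are used. Section 6.6.4 does not supply these either.

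A conversion does exist elsewhere. The footnote to Table 4 reads "Given that one unit of packed RBC typically will raise the hemoglobin concentration by 1 g/dL, an estimated decrease in hemoglobin will be calculated". It hangs on the hemoglobin and transfusion criterion for life-threatening bleeding in the VARC-2 table, and the section 6.6.2 endpoint does not refer to it.

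Blood counts are taken at screening, after device insertion but before activation (section 4.3.2), at the end of monitoring, where they "should be collected immediately before removal of the Saranas EBBMS", and again before discharge (section 4.3.3). For transfusion, section 4.3.3 lists "Recording of the number of units of blood transfused" without time or product. The number of transfusions and the VARC-2 grade are separate secondary endpoints against the same device level.

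**The concern.** The endpoint is meant to show whether a higher device level goes with more blood lost. Transfusion raises hemoglobin, and units given tend to follow units lost, so the raw drop can shrink most in the heaviest bleeders. With about 5 bleeds expected in 100 subjects (section 6.1), one such subject carries weight.

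The protocol expects transfusion in this setting. Of access-site bleeds noticed late, section 1.1 says "This often necessitates surgical intervention and/or blood transfusions to manage these complications". Monitoring runs for up to 8 hours after the procedure, which leaves time for units to be given before the pre-removal sample, and more before the discharge sample. One subject could then have two different hemoglobin drops in the same report: an estimated one for VARC-2 and a raw one here.

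**Working it through.** **The plan's own figure.** The only sizing figure is in section 6.1: kappa 0.74, 95% CI 0.39 to 1.0, with two discordant pairs. Cells 3/1/1/95 give observed agreement 0.98, chance agreement (4×4 + 96×96)/10,000 = 0.9232, and kappa (0.98 − 0.9232)/(1 − 0.9232) = 0.74. The large-sample interval is 0.393 to 1.086, capped at 1.0. The figure reproduces and does not involve hemoglobin. The plan states no figure for the hemoglobin endpoint.

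**Effect in one subject.** For loss L, u units given between the samples and a true rise of r g/dL per unit, the raw drop is L − u·r and the adjusted drop is L − u·r + u. The footnote gives r = 1; the range 0.7 to 1.3 is assumed. With L = 4 and u = 3:
- r = 1.0: raw 1.0, adjusted 4.0
- r = 0.7: raw 1.9, adjusted 4.9
- r = 1.3: raw 0.1, adjusted 3.1

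The raw value always falls below an untransfused 2 g/dL loss, and the adjusted value never does.

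**How often.** Section 1.1 gives three rates, all from other populations:
- "One percent of these procedures were associated with a bleeding complication at the access site severe enough to warrant blood transfusion"
- "1.8% of the patients had access site hematomas that necessitated transfusion"
- "5.4% of the patients had major bleeding" (and were transfused, with no bleeding site stated)

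The chance of at least one transfused subject in 100 is 1 − (1 − p)^100. The bias needs transfusion before the follow-up sample, so p is multiplied by the share s transfused in time. The documents do not give s; 25% to 50% is assumed.

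| p | any transfusion | s = 25% | s = 50% |
|---|---|---|---|
| 1% | 63% | 22% | 39% |
| 1.8% | 84% | 36% | 60% |
| 5.4% | 99.6% | 74% | 94% |

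**Effect on the correlation.** All inputs are assumed: device levels 0 to 3 in 95, 2, 2 and 1 subjects (Level 0 meaning no indicator triggered), mean loss 1 + level g/dL, noise SD 1 g/dL, r = 1, Pearson correlation. Section 6.1 supports only the 5 in 100, and it counts bleeds by either method, not device levels.
- Mean level = (2 + 4 + 3)/100 = 0.09. Variance of level = (2 + 8 + 9)/100 − 0.09² = 0.1819.
- Adjusted: covariance 0.1819 and variance of drop 1.1819, so the correlation is √(0.1819/1.1819) = 0.39.
- Raw, with u units to the one Level 3 subject: covariance 0.1819 − 0.0291u; variance of drop 1 + [10 + (3 − u)²]/100 − (0.09 − 0.01u)².
- u = 1: 0.1528/√(0.1819 × 1.1336) = 0.34
- u = 2: 0.1237/√(0.1819 × 1.1051) = 0.28
- u = 3: 0.0946/√(0.1819 × 1.0964) = 0.21

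Simulating 10,000 trials on these inputs gives the same means, and a 95% range of 0.22 to 0.54 for the adjusted correlation.

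**When adjustment does not help.** Let k Level 0 subjects lose 4 g/dL from a bleed away from the access site and receive 3 units (assumed). Their raw drop reads 1 g/dL, so the raw correlations above are unchanged. The adjusted covariance becomes 0.1819 − 0.0027k, and the variance of the drop 1 + (19 + 9k)/100 − (0.09 + 0.03k)².
- k = 3: 0.1738/√(0.1819 × 1.4276) = 0.34. The raw value is 0.39 with no units to the Level 3 subject and 0.34 with one.
- k = 4: 0.1711/√(0.1819 × 1.5059) = 0.33, against 0.34 raw with one unit to the Level 3 subject.
- With 2 or 3 units to the Level 3 subject, adjustment still gains 0.05 to 0.13.

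**The case against.** The strongest case is that the observed drop is a legitimate measure and that transfused heavy bleeders are not hidden: the number of transfusions and the VARC-2 grade are both related to the same device level. An adjusted drop is a composite that overlaps the transfusion endpoint. This stands and limits the importance of the point, but the other endpoints do not correct the hemoglobin result itself.

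A reader might infer that the plan ignores transfusion altogether. It does not. The Table 4 footnote commits to an estimated decrease; the gap is that nothing carries it to this endpoint. Some of the data may also exist already. VARC-2 grading needs whole blood or red cell units, section 5.1.1 asks for therapy given for adverse events, and section 4.3.2 asks for the investigator's actions after a detected bleed. The CRF is not among the documents.

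A reader might also take 63% to 99.6% as the chance that the endpoint is biased. Those figures count any transfusion, not one before the sample. The 5.4% is not stated to be access-site bleeding. Section 1.1 puts 23.8% of major bleeds in another registry at the access site; applying that share across registries (an assumption) gives 5.4% × 0.238 = 1.3%, and a 73% chance of any transfusion.

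Finally, attenuation toward zero is not assured. If Level 0 subjects are transfused for bleeding elsewhere, adjustment can be neutral or can dilute the access-site relationship. This objection stands, and it is a reason to report both drops rather than replace one with the other.

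**Conclusion.** The point holds in a limited form. Followed literally, section 6.6.2 understates loss by about 1 g/dL for each red cell unit given between the two samples, on the protocol's own conversion. That can reverse the severity order of individual subjects.

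The effect on the endpoint cannot be sized from the documents, which give no transfusion rate or timing for this population. On the assumed inputs, the correlation loses 0.06, 0.12 or 0.18 with 1, 2 or 3 units to one subject. The 1- and 2-unit results lie inside the adjusted estimate's own sampling range, and the 3-unit result sits at its edge. If no transfusion precedes the sample, nothing is lost. A reader might infer that the relationship would be largely erased; that needs heavy transfusion before the sample in most bleeders, which the documents neither state nor exclude.

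Severity is minor. This is one descriptive secondary endpoint, and the primary kappa analysis and the sample size do not depend on it. The change is a cheap improvement.

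**What to change.** In section 6.6.2, keep the observed drop and report beside it a transfusion-adjusted drop: baseline hemoglobin minus follow-up hemoglobin, plus 1 g/dL per red cell unit given between those two samples, citing the Table 4 footnote. Name both samples, for example the pre-activation sample as baseline and either the pre-removal or the discharge sample as follow-up. Record the time and product type of each transfusion, so that only red cell units given between the samples are added back.

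The cost is a sentence or two in section 6.6.2 and two data items per transfusion, if the CRF lacks them. Hemoglobin and unit counts are already collected. The data items should be settled before enrollment, because timing may not be recoverable later.

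The downsides are that the conversion is approximate, that units given for other reasons or for bleeding away from the access site are also added back, and that the measure overlaps the transfusion endpoint. Showing both drops lets the reader see whether the conclusion depends on the adjustment.
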